**Appendix B Schedule of Study Procedures (Part B – Screening to Week 48, SFU)**

Procedure a	Informed consent b	Screening	Treatment Period cd																Withdrawal	SFU	
		Before treatment initiation e D -28 to D -1 f	WK 1	WK 1	WK 1	WK 2	WK 3	WK 5	WK 9	WK 13	WK 17	WK 21	WK 25	WK 29	WK 33	WK 37	WK 41	WK 45		WK 49 g	30 to 40 days after the last dose
Allowable visit window			0	0	0	±1	±1	±2	±2	±2	±3	±3	±3	±3	±3	±3	±3	±3	±7	+7	
Confirmation of eligibility		X																			
Subject background d		X																			
Physical examination		X	X	X	X	X	X	X	X	X	X	X	X	X	X	X	X	X	X	X	X
Vital signs i		X	X		X	X	X	X	X			X						X	X	X	X
Weight/height k		X	X		X	X	X	X	X			X						X	X	X	X
ECOG performance status		X					X					X						X	X	X	X
12-lead ECG l		X	X n		X	X						X						X	X	X	X
Chest X-ray examination		X																			
Ophthalmology tests		X										X						X	X		
Imaging assessment m		X																X	X		
Bone density (DXA method)		X										X						X	X		
Hematology tests		X	X n				X	X	X			X			X			X	X	X	X
Blood biochemistry tests		X	X n				X	X	X	X	X	X	X	X	X	X	X	X	X	X	X
Blood lipid, sugar, etc. tests		X	X n				X	X	X			X						X	X	X	X
Urinalysis		X	X n				X	X	X			X						X	X	X	X
Heart-related tests		X	Measure as appropriate																		
Pharmacodynamic assessments		X	X o	X	X	X o			X o		X o	X									
Tumor marker		X					X	X	X	X	X	X			X			X	X		
BMP concentration p			X					X				X			X			X	X		
Pharmacokinetic assessments q			X	X	X	X	X	X	X	X	X	X			X			X	X r		

PGx sample collection		X (randomization through the treatment period)																	
QOL assessments	X	X					X	X	X		X	X				X	X	X	X
Concomitant medications/therapies	Collected from the time of informed consent until 30 to 40 days after the last dose																		
Adverse events, etc.	PTEs s		Information collected from study treatment initiation until 30 to 40 days after the last dose																
treatment	Oral doses once a day at least 30 minutes before breakfast																		

Abbreviations: WK = Week; D = Day; ECOG = Eastern Cooperative Oncology Group; PGx = pharmacogenomics; QOL = quality of life; SFU = safety follow-up

- a Unless otherwise specified, the assessments will be completed before study drug dosing.
- b Except for procedures that are normally part of a physical examination, subjects must sign the informed consent form before any study-related procedures are performed.
- c Additional examinations/assessments may be performed at the discretion of the investigator or sub-investigator.
- d Except for pharmacokinetic assessments, if the assessment and test results can be obtained, then the assessments will be performed before study treatment initiation.
- e Randomization will be performed by Day -1 (1 day before treatment initiation)
- f Day -1: Day before treatment initiation
- g If a subject is going to be switched to a GnRH agonist or a GnRH antagonist, this will be done after PK analysis sample collection and assessments have been completed.
- h Day 1: Day of treatment initiation
- i Including past and current medical history and previous therapeutic medications
- j Measurements will be taken after the subject has been sitting down for 5 minutes.
- k Height will be measured only at screening.
- l 12-lead ECG measurements will be taken after the subject has been lying down for at least 5 minutes.
- m Performed at screening only if imaging assessments were not performed within 28 days prior to treatment initiation, or if no usable images are available for the subject.
- n Results of tests performed up to 3 days before treatment initiation may be used as the D1 test results.
- o Blood samples will also be collected for the serum testosterone high sensitivity measurements. However, at WK1D1, only the high-sensitivity measurements will be performed.
- p Blood and urine sample collection
- q See Appendix E for detailed sample collection times
- r As a rule, blood samples will also be collected at withdrawal from the study.
- s Information will be collected from consent acquisition until treatment initiation.

**Appendix C Schedule of Study Procedures (Part B – Weeks 49 to 96)**

Procedure a	Continuation Treatment Period b					Withdrawal	SFU
	WK49 (WK48) D1 (D8)	WK61 D1	WK73 D1	WK85 D1	WK97 c D1		30 to 40 days after the last dose
Visit Day Allowable Window	±7	±7	±7	±7	±7	+7	
Physical examination	X	X	X	X	X	X	X
Vital signs d	X	X	X	X	X	X	X
Weight	X	X	X	X	X	X	X
ECOG performance status	X	X	X	X	X	X	X
12-lead ECG e	X		X		X	X	X
Imaging assessment	X				X	X	
Bone density (DXA method)	X		X		X	X	
Hematology tests	X	X	X	X	X	X	X
Blood biochemistry tests	X	X	X	X	X	X	X
Blood lipid, sugar, etc. tests	X	X	X	X	X	X	X
Urinalysis	X	X	X	X	X	X	X
Pharmacodynamic assessments	X	X	X	X	X	X	
Tumor marker	X	X	X	X	X	X	
QOL assessments	X	X	X	X	X	X	X
Concomitant medications/ therapies	Information collected until 30 to 40 days after the last dose						
Adverse events, etc.	Information collected until 30 to 40 days after the last dose						
treatment	Oral doses once a day at least 30 minutes before breakfast f						

Abbreviations: WK = Week; D = Day; ECOG = Eastern Cooperative Oncology Group; QOL = quality of life; SFU = safety follow-up

- a Unless otherwise specified, the assessments will be completed before study drug dosing.  
 b Additional examinations/assessments may be performed at the discretion of the investigator or sub-investigator.  
 c If a subject is going to be switched to a GnRH agonist or a GnRH antagonist, this will be done after PK analysis sample collection and assessments have been completed.  
 d Measurements will be taken after the subject has been sitting down for 5 minutes.  
 e Measurements will be taken after the subject has been lying down for 5 minutes.  
 f Study drug will not be taken at WK97D1.

**Appendix D Schedule of Blood Samples Collection for Pharmacokinetic Analysis (Part A)**

Time Point a	Dosing Time Point b													
	D1	D2	D3	D7	D12	D13	D14	D15	D21	D28	D29	D30	D31	D35
Before dosing c	X	X	X	X	X	X	X	X	X	X	X d	X e	X f	X g
0.5 hour (± 10 min) postdose	X						X							
1 hour (± 15 min) postdose	X						X			X				
1.5 hours (± 15 min) postdose	X						X							
2 hours (± 20 min) postdose	X		X	X			X			X				
4 hours (± 20 min) postdose	X						X			X				
6 hours (± 30 min) postdose	X						X							
8 hours (± 30 min) postdose	X						X			X				
12 hours (± 1 hour) postdose	X						X			X				

Abbreviations: D = day

- 
- a If a blood sample is going to be collected on an outpatient basis, then the subject will come in for the visit without taking the study drug.
  - b As a rule, a blood sample will be collected at discontinuation as well, but the blood sample for the post-treatment observation period will not have to be collected.
  - c Blood samples for PK analysis will be collected within 1 hour before dosing.
  - d 24 hours (± 1 hour) after dosing on D28
  - e 48 hours (± 4 hours) after dosing on D28
  - f 72 hours (± 4 hours) after dosing on D28
  - g Collected before starting the next treatment

**Appendix E Schedule of Blood Samples Collection for Pharmacokinetic Analysis (Part B)**

Time Point a	Dosing Time Point b												
	WK1			WK2	WK3	WK5	WK9	WK13	WK17	WK21	WK25	WK37	WK49
	D1 c	D2	D4	D1	D1	D1	D1	D1	D1	D1	D1	D1	D1
Before dosing d	X	X	X	X	X	X	X	X	X	X	X	X	X
2 hours postdose (± 20 min)	X					X							

Abbreviations: WK = week; D = day

- 
- a If a blood sample is going to be collected on an outpatient basis, then the subject will come in for the visit without taking the study drug.
  - b As a rule, blood samples will be collected at discontinuation as well.
  - c Blood samples will be collected after the subjects have taken the first dose of study drug at the hospital, and then eaten after an interval of at least 30 minutes, and then after another 2 hours have passed.
  - d Blood samples for PK analysis will be collected within 1 hour before dosing.

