A number of cardiac AEs according to Common Terminology Criteria for Adverse Events (CTCAE) were reported, but for these subjects the ECG interpretation was considered to be not clinically significant by the investigator. These cardiac AEs included electrocardiogram QT prolonged (1 AE in Part 1, 4 AEs in Part 2, and 7 AEs in Part 3) and first degree atrioventricular block (2 AEs in Part 1 and 6 AEs in Part 2). Changes in mean QTc interval of approximately 15 to 20 msec were noted before administration on Day 14 (80 to 180 mg QD) in adult male subjects in this study. The QTc changes were independent of drug administration, not correlated to drug levels, and are similar to those observed in surgical and medical castration studies with other

compounds. No major safety concerns were noted in healthy male subjects receiving single (80 to 360 mg) and multiple (20 to 180 mg) doses of TAK-385, and TAK-385 was well tolerated.

Single doses of 80 to 360 mg of TAK-385 administered orally (fasted state) were absorbed rapidly in plasma with median Tmax values ranging from 1.75 to 4.00 hours after administration across the entire dose range. After attaining Cmax, TAK-385 plasma concentrations declined in a multi-exponential manner with a mean T1/2 ranging from 19.1 to 21.7 hours. The mean Cmax and AUC values for TAK-385 generally increased in an approximately dose-proportional manner over the 80 to 360 mg dose range.

When a multiple dose of 20 to 180 mg QD of TAK-385 was administered, the drug was readily absorbed in plasma on Days 1 and 14, and Cmax typically occurred within 1 to 2 hours after dosing. After attaining Cmax, individual PK profiles on Day 14 exhibited a multi-exponential elimination phase with a mean elimination phase T1/2 of approximately 36 to 65 hours at doses of 20 to 180 mg QD. The trough concentration-time data (Day 2, and Days 11 to 14) implied that steady-state conditions were attained within approximately 10 days.

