### 9.1.21 Pharmacokinetic Assessments

The plasma concentrations will be measured at each blood sample collection time point (see [Appendix D](#) and [Appendix E](#)) in accordance with separately prepared written procedures.

The 3 time points for TAK-385 dosing that immediately precede blood sample collection, and the time points for the collection of blood samples for pharmacokinetic assessment, will be entered into the eCRF.

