When calculating Study Day relative to a reference date (i.e., date of first dose of study drug [Day 1]), if the date of the observation is on the same date or after the reference date, it will be calculated as: date of observation - reference date + 1; otherwise, it will be calculated as: date of observation - reference date. Hence, reference day is always Day 1 and there is no Day 0. When calculating Study Time relative to a reference time (i.e., time of each dose of study drug), it will be calculated as: time of observation - reference time.

When calculating Follow-up Day relative to a reference date (i.e., date of last dose of study drug [Follow-up Day 0]), it will be calculated as: date of observation - reference date. Hence, reference day is always Follow-up Day 0.

All evaluable data (i.e., non-missing and acceptable according to the Handling Rules for Analysis Data) will be handled according to the following rules.

For each visit, observation obtained in the corresponding time interval will be used. If more than one observation lies within the same visit window, the observation with the closest Study Day/Study Time to the scheduled Study Day/Study Time will be used. If there are two observations equidistant to the scheduled Study Day/Study Time, the later observation will be used. This does not apply to the end of study visit. For the end of study visit, the last observation obtained in the corresponding time interval will be used.

<Part A>

PSA

Visit	Scheduled Study Day (days)	Time Interval (days) Study Day
Baseline (Week 0)	Study Day: 1	-28 - 1
D28	Study Day: 28	2 - 35

Pharmacokinetic Assessments

		Time In	terval
Visit	Scheduled Study Time (hours)	Study Day (days)	Study Time (hours)
D1	-1	1	-3.00 - 0.00
D1	0.5	1	0.33 - 0.67
D1	1	1	0.75 - 1.24
D1	1.5	1	1.25 - 1.74
D1	2	1	1.75 - 2.33
D1	4	1	3.67 - 4.33
D1	6	1	5.50 - 6.50
D1	8	1	7.50 - 8.50
D1	12	1	11.00 - 13.00
D2	-1	2	-2.00 - 0.00
D3	-1	3	-2.00 - 0.00
D3	2	3	1.67 - 2.33
D7	-1	7	-2.00 - 0.00
D7	2	7	1.67 - 2.33
D12	-1	12	-2.00 - 0.00
D13	-1	13	-2.00 - 0.00
D14	-1	14	-2.00 - 0.00
D14	0.5	14	0.33 - 0.67

		Time In	terval	
Visit	Scheduled Study Time (hours)	Visit Scheduled Study Time (hours) (days)		Study Time (hours)
D14	1	14	0.75 - 1.24	
D14	1.5	14	1.25 - 1.74	
D14	2	14	1.75 - 2.33	
D14	4	14	3.67 - 4.33	
D14	6	14	5.50 - 6.50	
D14	8	14	7.50 - 8.50	
D14	12	14	11.00 - 13.00	
D15	Study Day: 15	15	16.00 - 34.00 (from last dose)	
D21	Study Day: 21	18 - 24	16.00 - 34.00 (from last dose)	

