3.2.2 Pharmacokinetic Parameters

Listing			
Analysis Set:	Full Analysis Set		
Analysis			
Variable(s) :	D1: AUC _{τ} , C _{max} and t _{max}		
	D14: AUC _{last, ss} , AUC _{t, ss} , AUC _{t, ss} /D, C _{max, ss} , C _{max, ss} /D, C _{min, ss} , t _{max, ss}		

D28: AUC_{last, ss}, AUC_{τ , ss}, AUC_{τ , ss}/D, CL/F_{ss}, C_{max, ss}, C_{max, ss}/D, t_{max, ss}, t_{1/2z}, V_z/F_{ss}, λ_z , number of data points with first and last data points used in the terminal disposition phase regression analysis and adjusted R² (coefficient of determination) for the terminal disposition phase regression analysis

Analytical

Method(s): PK parameters will be calculated by using individual plasma concentrations with actual sampling times. Plasma concentrations from D1 to D2, D14 to D15 and D28 to D35 will be used for the calculation of PK parameters on D1, D14 and D28 respectively. Plasma concentrations deviated from the visit window will be also used for the calculation. A standard non-compartmental analysis will be performed using the linear trapezoidal rule. If subject received prohibited concomitant medications, therapies or foods, then the plasma concentrations measured on and after this day will be used to estimate the PK parameters for the listing but the results will be treated as reference values.

Individual PK parameters will be listed. The listings will include the treatment group, subject ID and evaluation day (D1, D14, and D28) in addition to the PK parameters.

Descriptive Statistics

Analysis Set:	Pharmacokinetic Analysis Set		
Analysis	D1:	AUC_{τ} , C_{max} and t_{max}	
Variable(s) :	D14:	$AUC_{last, ss}, AUC_{\tau, ss}, AUC_{\tau, ss}/D, C_{max, ss}, C_{max, ss}/D, C_{min, ss}, t_{max, ss}$	
	D28:	$AUC_{last, ss}, AUC_{\tau, ss}, AUC_{\tau, ss}/D, CL/F_{ss}, C_{max, ss}, C_{max, ss}/D, t_{max, ss} , t_{1/2z},$	
		$V_z/F_{ss}, \lambda_z$	

Analytical

Method(s) : For the pharmacokinetic parameters, the number of subjects, mean, SD, min, median, max, geometric mean, and CV will be provided for each treatment group. PK parameters which are treated as reference values will be excluded from the summary statistics.

Graphical assessment of dose-proportionality on $C_{max, ss}$ and $AUC_{\tau, ss}$ will be conducted on D14 and D28 by plotting individual dose-normalized exposure parameters, i.e., $C_{max, ss}/D$ or $AUC_{\tau, ss}/D$ versus dose.

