4.2 Pharmacokinetic Analysis

4.2.1 Plasma Concentrations

Analysis Set: Analysis	Pharmacokinetic Analysis Set		
Variable(s) :	Plasma concentrations of TAK-385 (ng/mL)		
Visit :	WK1D1 and WK5D1: Before dosing and 2 hours after dosing.		
	WK1D2, WK1D4, WK2D1, WK3D1, WK9D1, WK13D1, WK17D1,		
	WK21D1, WK25D1, WK37D1 and WK49D1: Before dosing		
Analytical			
Method(s) :	Descriptive statistics, geometric mean, and CV will be used to summarize		
	plasma concentrations at each visit for each treatment group.		
	Case plots as well as the mean and standard deviation plots of changes over		
	time will be provided for plasma concentrations for each treatment group.		

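### Part B Week 1 Day 1 post-dose PK sample: footnote c puts the draw at least 2.5 h after dosing, outside both the protocol's 2 h ± 20 min and the SAP window of 1.75–2.33 h

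*Protocol*

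**What the plan says.** Protocol Appendix E has a single post-dose row for Part B, ticked at Week 1 Day 1 and Week 5 Day 1. It places the draw 2 hours after dosing, plus or minus 20 minutes. Footnote c is attached to the Week 1 Day 1 column only. Under it, blood is collected once subjects have taken the first dose at the hospital, "and then eaten after an interval of at least 30 minutes, and then after another 2 hours have passed".

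The SAP lists the visits in Section 4.2.1 as "WK1D1 and WK5D1: Before dosing and 2 hours after dosing" and summarises concentrations by visit and treatment group. Its Definition of Visit Window counts Study Time from the dose and states: "For each visit, observation obtained in the corresponding time interval will be used". In the Part B pharmacokinetic table, the post-dose window is 1.75–2.33 h at Week 1 Day 1 and 1.67–2.33 h at Week 5 Day 1.

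SAP Section 3.2.2 has one sentence that keeps off-window samples: "Plasma concentrations deviated from the visit window will be also used for the calculation". It sits in the Part A section on PK parameters. The SAP plans no PK parameters for Part B.

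**The concern.** Two instructions in the same protocol table give the same sample different times, and the later of the two lies outside the window the SAP uses to accept it. A site that follows the footnote exactly would produce a valid concentration with no window to enter.

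Plasma concentration is a Part B secondary endpoint. Both planned Part B groups receive the 320 mg loading dose, and this is the only Part B sample near the peak after it. Protocol Section 4.1.2.5 reports single-dose "median Tmax values ranging from 1.75 to 4.00 hours after administration", so a shift from 2 h to 2.5 h or later falls where concentrations may still be changing. Because Week 5 Day 1 carries no such footnote, the two samples labelled 2 h could also represent different times since dose.

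**Working it through.** **Inputs**

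- Footnote c (Appendix E): at least 30 min from dose to meal, then a further 120 min.
- Post-dose row (Appendix E): 120 ± 20 min from dosing.
- SAP window, Week 1 Day 1: 1.75–2.33 h from dosing.
- SAP window, Week 5 Day 1: 1.67–2.33 h from dosing.
- Meal lengths, and gaps longer than 30 min, are not given in the documents. They are assumed below only to show a range.

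**Protocol row.** 120 − 20 = 100 min and 120 + 20 = 140 min, i.e. 1.67–2.33 h. This reproduces the SAP's Week 5 Day 1 window and the upper limit of its Week 1 Day 1 window.

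**Footnote c.** Draw time = gap + meal length + 120 min. The minimum, with no time for the meal, is 30 + 0 + 120 = 150 min = 2.50 h.

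| Dose-to-meal gap | Meal length | Draw time | Beyond 140 min |
|---|---|---|---|
| 30 min (minimum) | 0 | 2.50 h | 10 min |
| 30 min | 15 min (assumed) | 2.75 h | 25 min |
| 30 min | 30 min (assumed) | 3.00 h | 40 min |
| 60 min (assumed) | 30 min (assumed) | 3.50 h | 70 min |

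No case falls inside either window. Two departures from the footnote's wording would bring the draw inside:

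- counting the 2 hours from the dose (2.00 h), which ignores the word *another*;
- moving the row's tolerance onto the footnote (150 − 20 = 130 min = 2.17 h), although the footnote requires the 2 hours to have passed.

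**What the SAP does with a 2.5 h draw.** Only two windows exist at Week 1 Day 1: pre-dose (−3.00 to 0.00 h) and 1.75–2.33 h. A draw at 2.5 h enters neither.

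**Lower limit.** The row starts at 100 min; the SAP's Week 1 Day 1 window starts at 1.75 × 60 = 105 min. So 5 of the row's 40 allowed minutes (12.5%) comply with the protocol but miss the SAP window. This is a share of minutes, not an expected share of samples. In Part A the SAP uses 1.75 h on Days 1 and 14, where a 1.5 h sample (1.25–1.74 h) has to be kept separate, and 1.67 h on Days 3, 7 and 28, where there is none. Part B has no 1.5 h sample.

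**The case against.** The footnote may be a drafting or translation slip for 2 hours after the dose. Appendix J of Amendment 1 marks some corrections as not applying to the English protocol, so the English text is evidently a translation. Footnote c also covers the whole Week 1 Day 1 column, including the pre-dose sample, so it cannot be read entirely literally. The row and SAP Section 4.2.1 agree on 2 hours, and Amendment 1 added the tolerance to that row. All this makes a slip plausible. It does not remove the conflict: sites act on the text, and no other passage says which instruction governs.

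Exclusion is also not certain. The Handling Rules for Analysis Data are a separate document and could contain a relevant rule, and the SAP does not say whether individual case plots drop off-window samples. This is a fair limit. But the Definition of Visit Window applies its intervals to data already acceptable under those rules, so acceptability alone does not put a 2.5 h draw into the summary.

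The harm is small, and that stands in full. This is 1 of 15 scheduled Part B PK samples per subject (Table 9.c), used descriptively. On the cited Tmax range a draw at 2.5–3.0 h may still be near peak. The range of 0 to 30 affected samples is simply every possibility. The lower-limit mismatch is trivial on its own and has no bearing on a draw that is late; SAP windows differ from protocol tolerances elsewhere too.

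**Conclusion.** The concern holds, as an internal inconsistency. On its plain wording, footnote c requires a draw at 2.5 h or later, while the row allows 1.67–2.33 h and the SAP 1.75–2.33 h. The ranges do not overlap, and the gap to the row's upper limit is at least 10 minutes, or 25–40 minutes if a meal of 15–30 minutes is assumed.

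On the SAP as written, a sample drawn by the footnote is left out of the Week 1 Day 1 2 h summary. Between 0 and 30 of the 30 planned samples could be lost from it; the documents give no way to narrow that. The conclusion assumes that the Handling Rules, which are not among the documents, do not override the window.

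Primary safety endpoints are unaffected. The Week 1 Day 2 pre-dose sample still follows the loading dose, and Part A gives full Day 1 profiles after 320 mg in Cohorts 1 to 3.

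**What to change.** Reconcile footnote c, the Appendix E row and the SAP's nominal time and window so that all give one sampling time counted from dosing. In the same edit, settle one lower limit for the Week 1 Day 1 window (1.75 h or 1.67 h).

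For samples already drawn outside the window, report the Week 1 Day 1 concentrations against actual time since dose instead of leaving them out. The data exist: under protocol Section 9.1.21 the eCRF holds "The 3 time points for TAK-385 dosing that immediately precede blood sample collection", together with the sampling times.

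The cost is one footnote and one SAP window line, plus a listing or plot by actual time if off-window samples exist. No additional blood samples are needed.

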## Appendix F Responsibilities of Principal Investigator

1. Conduct the appropriate study in accordance with the protocol and GCP considering the rights, safety and wellbeing of human subjects.
2. When a part of the important activities related to the study are delegated to the sub-investigator or the study support staff, prepare the lists of activities to be delegated and responsible personnel, submit the lists to the head of the site in advance to get them accepted.
3. Prepare a written informed consent form and other written information, and update as appropriate.
4. Confirm the contents of the Clinical Study Agreement.
5. Provide necessary information on the protocol, drugs and responsibilities of individual personnel to the sub-investigator and study support staff, and provide guidance and supervision.
6. Screen subjects who meet the requirements of the protocol, provide the explanation of the study in writing and obtain the written consent.
7. Assume responsibility for all the medical judgement related to the study.
8. Ensure in collaboration with the head of the site that sufficient information on all clinically significant adverse events related to the study are provided to subjects throughout and beyond the period when subjects participate in the study.
9. If a subject consult other medical institution or other department, notify the physician of the medical institution or department of the subject's participation in the study, as well as the end and termination of the study in writing, and document such records.
10. In case of urgent report of a SAE, immediately notify the head of the site and the sponsor in writing.
11. Prepare correct and complete eCRFs, and submit them to the sponsor with electronic signature.
12. Check and confirm the contents of eCRFs prepared by the sub-investigator or transcribed from the source data by the study support staff, and submit them to the sponsor with electronic signature.
13. Discuss any proposal from the sponsor including update of the protocol.
14. Notify the head of the site of the end of the study in writing.

